3.0 STUDY ENDPOINTS

3.1 Primary Effectiveness Endpoint

The primary effectiveness endpoint is freedom from any documented AF, atrial flutter, or atrial tachycardia lasting >30 seconds duration through the 12-month follow-up visit in the absence of Class I or III AADs (with the exception of previously failed AADs at doses not exceeding those previously failed).

Any arrhythmia that occurs within the blanking period or during the “AAD Optimization Period” visit will not be considered a failure (Visit 5 up to Visit 10). The rhythm status used for evaluation of this endpoint shall be derived from regularly scheduled monitoring (i.e., Holter, Zio™ Patch, or 30 second ECG), as well as any symptom driven monitoring that is performed.

The following scenarios shall constitute a failure of the primary effectiveness endpoint:

1. Any documented AF, atrial flutter, or atrial tachycardia lasting >30 seconds duration) that occurs at any time beginning at the 6-month visit and through the 12-month visit.
2. Any previously failed class I or III AAD administered at a dose higher than baseline and between the 6-month visit and the 12-month visit.
3. Any newly introduced class I or III AAD usage beginning at the 6-month visit through the 12-month visit.
4. DC cardioversion for AF, atrial flutter, or atrial tachycardia that takes place at any time beginning at the 6-month visit through the 12-month visit.
5. Catheter ablation or surgical treatment for AF, atrial flutter, atrial tachycardia that takes place at any time beginning at the 3-month visit and ending at the 12-month visit.
6. Two or more repeat catheter ablations within the 2nd blanking period
7. The use of a non-study device for creation of any lesions during the surgical epicardial ablation procedure

For the purposes of this study, atrioventricular nodal reentrant tachycardia (AVNRT), inappropriate sinus tachycardia, and Wolff–Parkinson–White syndrome (WPW) will not be considered procedure failures.

For this study, AtriCure defines failure of an antiarrhythmic drug (AAD) to include ineffectiveness or intolerance of the AAD.

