2.1.1 Primary Effectiveness Endpoint

The primary effectiveness endpoint is freedom from any documented AF, atrial flutter, or atrial tachycardia lasting >30 seconds in duration through the 12-month follow-up visit in the absence of Class I or III AADs (with the exception of previously failed AADs at doses not exceeding those previously failed).

Any arrhythmia that occurs within the blanking period or the AAD Optimization period will not be considered a failure (Visit 5 up to Visit 10). The rhythm status used for evaluation of this endpoint will be derived from regularly scheduled monitoring (i.e. Holter, Zio™-Patch, or 30 second ECG) as well as any symptom driven monitoring that is performed.

The following scenarios shall constitute a failure of the primary effectiveness endpoint:

1. Any documented AF, atrial flutter, or atrial tachycardia lasting >30 seconds duration that occurs at any time beginning at the 6-month visit and through the 12-month visit. These will be

Statistical Analysis Plan		Page 6 of 22
Sponsor	Study	Version
AtriCure	DEEP Pivotal Study	Version 2.0

documented on any Core Lab – ECG form with a time interval of “6 Month Post Endocardial” or “12 Month Post Endocardial”.

2. Any previously failed class I or III AAD administered at a dose higher than baseline and between the 6-month visit date plus one day and the 12-month visit date.
3. Any newly introduced class I or III AAD usage beginning at the 6-month visit date plus one day and through the 12-month visit date.
4. DC cardioversion for AF, atrial flutter, or atrial tachycardia that takes place at any time beginning at the 6-month visit date and ending at the 12-month visit date.
5. Catheter ablation or surgical treatment for AF, atrial flutter, atrial tachycardia that takes place at any time beginning at the 3-month visit date and ending at the 12-month visit date.
6. Two or more repeat catheter ablations within the 2nd blanking period.
7. The use of a non-AtriCure study device for creation of any lesions during the surgical epicardial ablation procedure.

For the purposes of this study, atrioventricular nodal reentrant tachycardia (AVNRT), inappropriate sinus tachycardia, and Wolff–Parkinson–White syndrome (WPW) will not be considered procedure failures.

For this study, AtriCure defines failure of an antiarrhythmic drug (AAD) to include ineffectiveness or intolerance of the AAD.

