5.6.1 Primary Effectiveness Endpoint

The primary effectiveness endpoint is freedom from any documented AF, atrial flutter, or atrial tachycardia lasting >30 seconds in duration through the 12-month follow-up visit in the absence of Class I or III AADs (with the exception of previously failed AADs at doses not exceeding those previously failed). Effectiveness failure events are described in detail in section 2.1.1.

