5.6.1.1 Primary Analysis

The statistical analysis of the primary effectiveness endpoint will consist of a comparison of the proportion of patients who remain a primary effectiveness success at the 12-month visit to a historical control rate that is based on results from the feasibility trials and published literature. The primary effectiveness endpoint will be assessed with the following hypothesis:

$$H_0: p_E \leq 0.60$$

$$H_a: p_E > 0.60$$

where p_E = the proportion of primary effectiveness success. The hypothesis will be evaluated using a one-sided chi-squared test at a one-sided $\alpha=0.025$ level of significance. The objective will be met if the estimated one-sided p-value is < 0.025. The mITT population will be the primary population for this analysis. Missing values will be treated as described in the Missing Values section 5.3 with the primary method being the LOCF method.

The proportion of primary effectiveness successes will be calculated with subjects as the experimental unit (i.e., the subject will be considered a success if no primary effectiveness failure was recorded from the 6-month visit through the 12-month visit). The numerator of the proportion will be the number of subjects who are a primary effectiveness success, and the denominator will be the total number of subjects. The endpoint will be presented with the numerator and denominator, the proportion and its 95% two-sided exact binomial confidence interval, and the one-sided p-value.

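### The scoring rule for primary effectiveness counts only failures from the 6- to the 12-month visit, so it drops earlier failures that the endpoint definition lists and can only raise the success rate

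*SAP*

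**What the plan says.** SAP 2.1.1 gives seven scenarios under the lead-in "The following scenarios shall constitute a failure of the primary effectiveness endpoint". Each has its own timing:

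- Scenarios 1 to 4 (arrhythmia, higher-dose AAD, new AAD, cardioversion) run between the 6-month and 12-month visits.
- Scenario 5, catheter ablation or surgical treatment, counts if it "takes place at any time beginning at the 3-month visit date and ending at the 12-month visit date".
- Scenario 6 is "Two or more repeat catheter ablations within the 2nd blanking period".
- Scenario 7 is "The use of a non-AtriCure study device for creation of any lesions during the surgical epicardial ablation procedure".

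SAP 5.6.1 refers back to this list: "Effectiveness failure events are described in detail in section 2.1.1". SAP 5.6.1.1 then explains how a subject is scored: "the subject will be considered a success if no primary effectiveness failure was recorded from the 6-month visit through the 12-month visit". Protocol 9.7.1 has the same parenthesis. The missing-data text in SAP 5.3 and Protocol 9.9 uses the same 6- to 12-month window when it says who is a failure under every imputation method.

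**The concern.** The scoring parenthesis applies one window to all failures, while the endpoint definition gives each failure its own. Taken literally, scenarios 6 and 7 could never count, and scenario 5 would lose the part between the 3- and 6-month visits. This is the only place in the analysis section that says in words when a subject is a success, and it stands directly before the numerator that is tested against 60%. A programmer who follows it would score some defined failures as successes. None of the planned sensitivity analyses would reveal this, because they vary the imputation and the population, not the failure window.

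**Working it through.** **Windows side by side**

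| Scenario (SAP 2.1.1) | When it can occur | Counted by the parenthesis? |
|---|---|---|
| 1 to 4 | 6- to 12-month visit (2 and 3 from the next day) | Yes |
| 5 | 3- to 12-month visit | Only from the 6-month visit |
| 6 | 90 days after the endocardial procedure | No |
| 7 | Epicardial operation | No |

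The failures counted by the parenthesis are a strict subset of the list. The denominator is the same under both readings, because the mITT definition in SAP 5.2 does not remove subjects with an early failure. The literal success count is therefore never below the list-based count. It is higher whenever a subject's only failure is scenario 6, scenario 7, or scenario 5 before the 6-month visit.

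**Can such subjects occur?** Protocol 7.9 allows one additional endocardial procedure in the 2nd blanking period, so scenario 6 needs a departure from the protocol. Scenario 7 needs a lesion device outside the specified set. Protocol 5.3.5 encourages re-intervention during blanking but permits it at any time if medically necessary, so a scenario 5 ablation between months 3 and 6 is possible.

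**The plan's own sample size.** Protocol 9.3 gives 182 for 60% against 70%, one-sided 0.025, 80% power:

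n = [(1.960·√(0.6·0.4) + 0.842·√(0.7·0.3)) / 0.10]² = 181.1, so 182.

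This reproduces the figure, but without the continuity correction the protocol names; with it, n = 191.0, so 192. That is a side observation and does not affect this point.

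**Decision boundary.** Inputs are p0 = 0.60 and one-sided 0.025. Three values of N are shown because the mITT number is unknown: 220 (maximum treated), 182 (required), and 176 (220 × 0.80, the planned 20% attrition). The exact p is P(X ≥ x) for X ~ Bin(N, 0.60). The chi-squared p is the upper normal tail of z = (x − 0.60N)/√(0.24N), without continuity correction. The protocol names the exact test and the SAP the chi-squared test; both give the same critical counts.

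| Successes | Exact p | Chi-squared p | Result |
|---|---|---|---|
| 146/220 | 0.031 | 0.027 | misses |
| 147/220 | 0.022 | 0.020 | meets |
| 122/182 | 0.030 | 0.026 | misses |
| 123/182 | 0.021 | 0.018 | meets |
| 118/176 | 0.033 | 0.028 | misses |
| 119/176 | 0.023 | 0.020 | meets |

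**Chance that the two readings disagree.** Suppose k subjects fail only under the full list. With critical count c, the verdicts differ when the list-based count falls from c − k to c − 1, so the probability is P(c − k ≤ X ≤ c − 1) with X ~ Bin(N, p).

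| N | k=1, p=0.60 | k=1, p=0.70 | k=2, p=0.60 | k=2, p=0.70 |
|---|---|---|---|---|
| 220 | 0.9% | 2.9% | 2.0% | 5.3% |
| 182 | 0.9% | 4.3% | 2.1% | 8.0% |
| 176 | 1.0% | 4.5% | 2.3% | 8.3% |

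The values k = 1 and k = 2 are illustrations, not estimates.

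**Do the lists agree?** Not fully. Scenario 3 starts at the 6-month visit in Protocol 3.1, but in SAP 2.1.1 it counts "beginning at the 6-month visit date plus one day and through the 12-month visit date"; scenario 2 has the same one-day shift in the SAP. For scenario 7, Protocol 3.1 has "The use of a non-study device for creation of any lesions during the surgical epicardial ablation procedure", whereas the Protocol synopsis agrees with the SAP wording. A bare pointer to the list would therefore leave open which list governs.

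**The case against.** The strongest reply is that the surrounding text already settles the intent. SAP 5.6.1.1 opens by speaking of patients who are still a success at 12 months, and someone who has met a defined failure can hardly still be one. SAP 5.6.1 sends the reader to section 2.1.1. The LOCF rule uses status up to the last test, and the worst- and best-case rules mention failure without any window. The parenthesis can be read as a loose gloss, since the numerator in the next sentence is simply the number of successes. The missing-data sentence says who is certainly a failure; it does not turn earlier failures into successes.

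Much of this stands. The full list is the likely intent, and the missing-data sentence alone is not an error. The boundary figures are also generic, since one subject at the boundary flips any binary test, and exposure is probably confined mainly to scenario 5 between months 3 and 6. Two reservations apply to the list differences. Protocol 3.1 words scenario 2 as lying between the two visits, so its exact start day is less clear than for scenario 3. The SAP also cites a Revision H dated 28 September 2022, while the protocol at hand is Revision H of 11 May 2021, so some differences between the documents may come from a version not seen here. The scenario 7 difference lies within the protocol itself, so that does not explain it.

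What does not stand is that the text resolves itself. No sentence overrides the stated window, and the rule for the primary numerator should allow only one way of programming it.

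**Conclusion.** The concern holds: the scoring sentence is wrong as written. It contradicts the endpoint's own failure list, and any error it causes favours success. The intended rule can be recovered, and the effect is probably small. Its size cannot be computed, because the documents give no rate for early failures in subjects who then pass every check from month 6 to month 12, and the mITT number is unknown. If there are no such subjects, nothing changes. With one, the verdict would differ in about 1% of trials at a true 60% and in 2.9% to 4.5% at 70%, over N from 220 down to 176. This should be fixed before the analysis is programmed.

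**What to change.** 1. Reconcile the failure lists in the Protocol synopsis, Protocol 3.1 and SAP 2.1.1 (start day of scenarios 2 and 3, device wording of scenario 7), so that one list governs.
2. In SAP 5.6.1.1, replace the parenthesis with: *the subject is a success if none of failure scenarios 1–7 of SAP section 2.1.1 occurred in the time window stated for that scenario.*
3. In SAP 5.3, write: *a subject meeting any of scenarios 1–7 of section 2.1.1 in its stated window is a failure under all methods below.*
4. Make the matching changes in Protocol 9.7.1 and 9.9, pointing to the reconciled list.

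The edits to SAP 5.3 and Protocol 9.9 are for consistency; those to SAP 5.6.1.1 and Protocol 9.7.1 are essential. The cost is one sentence in each of four places and three scenario wordings to align. Sample size and test stay the same. The reported success rate may be slightly less favourable than under the literal rule.

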5.6.1.2 Sensitivity Analysis

Sensitivity analyses for the primary effectiveness are discussed in the sections of this SAP related to missing data (different imputation schemes) and analysis populations (i.e., PP analysis).

5.6.2 Primary Safety Endpoint

The primary safety endpoint is a composite endpoint consisting of any one or more of events described in section 2.1.2 if they are adjudicated by the CEC to be serious adverse events (SAEs) and related to device/procedures.

Statistical Analysis Plan		Page 14 of 22
Sponsor	Study	Version
AtriCure	DEEP Pivotal Study	Version 2.0

5.6.2.1 Primary Analysis

The statistical analysis of the primary safety endpoint will consist of a comparison of the proportion of patients who fail to complete the trial without a primary safety endpoint event to a historical control rate that is based on results from the feasibility trials. Adverse events will be adjudicated in accordance with the CSP. The primary safety endpoint will be assessed with the following hypothesis:

$$H_0: p_s \geq 0.28$$

$$H_a: p_s < 0.28$$

where p_s = the proportion of primary safety failures in the safety population. The hypothesis will be evaluated using a one-sided statistical test using the normal approximation to the binomial distribution. A Z-test will be conducted at a one-sided $\alpha=0.025$ level of significance to test the hypothesis. The objective will be met if the estimated one-sided p-value is < 0.025 . The safety population will be the primary population for this analysis. Missing values will be treated as described in the Missing Values section 5.3. If a subject misses a follow-up visit and cannot subsequently be contacted to determine their primary safety status, the primary safety endpoint will be considered a failure and the subject will be excluded from any subsequent secondary safety analyses for which their status is unknown.

The proportion of primary safety failures will be calculated with subjects as the experimental unit (i.e., the subject will be considered a failure if a primary safety event was experienced within the timeframes defined in the endpoint). The numerator of the proportion will be the number of subjects who have a primary safety event and the denominator will be the total number of subjects. The endpoint will be presented with the numerator and denominator, the proportion and its 95% two-sided normal approximated confidence interval, and the one-sided p-value.

5.6.3 Secondary Effectiveness Endpoints

Analysis of secondary effectiveness endpoints will be based on descriptive statistics and nominal two-sided 95% confidence intervals for observed data, with methods as described in section 5.1.1. Secondary Effectiveness Endpoint #1 will be evaluated with a hypothesis test. The remaining secondary endpoints will be presented as exploratory analyses; no statistical inference will be performed.

5.6.3.1 Secondary Effectiveness Endpoint #1

The statistical analysis of secondary effectiveness endpoint #1 will consist of a comparison of the proportion of patients with LAA exclusion at the 12 Month Visit is statistically significantly higher than 80%, which will exceed the 77.5% expectation of success based on other exclusion methods, with less risk of injury than those methods. The primary effectiveness endpoint will be assessed with the following hypothesis:

$$H_0: p_2 \leq 0.80$$

Statistical Analysis Plan		Page 15 of 22
Sponsor	Study	Version
AtriCure	DEEP Pivotal Study	Version 2.0

$$H_a: p_2 > 0.80$$

where p_2 = the proportion of subjects with LAA exclusion at the 12-month Visit. LAA exclusion is defined as a lack of fluid communication (<3 mm residual communication with LAA and < 10mm residual pocket) between the LA and LAA. The hypothesis will be evaluated using a one-sided statistical test. An exact, one-sample binomial test will be conducted at a one-sided $\alpha=0.025$ level of significance to test the hypothesis. The objective will be met if the estimated one-sided p-value is < 0.025. The AtriClip effectiveness population will be the primary population for this analysis. The LOCF method will be utilized for patients who do not have TEE testing at the 12-Month visit.

The proportion will be calculated with subjects as the experimental unit. The numerator of the proportion will be the number of subjects with LAA exclusion at the 12-month Visit and the denominator will be the total number of subjects. The endpoint will be presented with the numerator and denominator, the proportion and its 95% two-sided exact binomial confidence interval, and the one-sided p-value.

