Visit Timepoint / Window	Up to 45 days		2-3 days post Epi	+/- 2 Days	30 days +7	91-121 days post Epi	1 day post Endo	7 days post Endo +1	30 days post Endo +7	90 days +14	180 days +/- 30	Symptom or Test	365 days + 30	Year +/- 60 days	Approx. 6 Mo post Annual Visit	Exit
Primary Effectiveness Endpoint														X		
Telephone Contact				X ²⁴				X							X	
Occurrence of AF/AFL/AT – Health Economic Endpoints														X	X	
Study Exit																X

¹ See **Subject Visits** for tests to be conducted at each visit.

² Anticoagulation testing to be performed in accordance with institutional SOC depending on subject's anticoagulation therapy.

³ LAA exclusion verification only for subjects that had the AtriClip placed during Epicardial Surgical Ablation Procedure. These data are submitted to a core lab.

⁴ AF Classification Form must be completed and submitted to sponsor for review prior to Epicardial Surgical Ablation Procedure

⁵ Urine or serum pregnancy test - females of childbearing potential (**within 7 days prior to the surgical procedure**).

⁶ Collection/analysis completed within 7 days of procedure.

⁷ Must be conducted within 120 days prior to the Epicardial Surgical Ablation Procedure.

⁸ In subjects with a documented history of pulmonary compromise.

⁹ Must be conducted within 60 days prior to the Epicardial Surgical Ablation Procedure.

¹⁰ Anticoagulation/antiplatelet therapies administered per SOC.

¹¹ Intraoperative confirmation that no clot is present in LAA.

¹² CT/MR Imaging performed only if subject exhibits symptoms suggestive of pulmonary vein stenosis. Use same imaging technique performed at baseline imaging to the extent possible.

¹³ Only health status will be collected.

¹⁴ For example, cardioversion for subjects in atrial fibrillation per physician discretion.

¹⁵ A Holter or Zio™ Patch will be worn by all subjects.

¹⁶ Conducted prior to surgical procedure to rule out LA/LAA thrombus and post LAA management to confirm exclusion of LAA.

¹⁷ See **Subject Visits 12-15** for details of events of interest to be collected.

¹⁸ CTA imaging of the LAA performed only in those subjects that had the AtriClip placed during the Epicardial Surgical Ablation Procedure. Pulmonary veins will also be

CONFIDENTIAL

Protocol Number: CP-2014-1

Protocol Name: DEEP Pivotal

Version: Rev H; 11May2021

Page 21 of 129

assessed, and CTA will be utilized.

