7.14 Visit 11 – 12 Month Post Endocardial EP Ablation Procedure

A follow-up evaluation will be scheduled for **12 months (365 days + 30 days)** post Endocardial EP ablation procedure. The following will be conducted and/or obtained at the 12 Month Visit:

- AFEQT Questionnaire

- Targeted Physical Examination
- Weight
- Blood Pressure and Heart Rate
- NYHA Class
- RBC, WBC, HGB, HCT, Platelets, BUN (Urea), Creatinine
- Heart Rhythm Assessment – 30 second ECG
- 24-Hour Continuous ECG Monitoring/ Arrhythmia Monitoring - Holter or ZioTM Patch
- Concomitant procedures to treat arrhythmia (i.e., cardioversion for subjects in atrial fibrillation), performed at physician discretion
- Medications Review
- Anticoagulation Testing in accordance with institutional SOC (e.g., INR for subjects on warfarin or aPTT or ECT if on dabigatran)
- Adverse Event Assessment
- Collect symptom driven monitor from subject at this visit and ensure subject's data has been uploaded to core laboratory for rhythm assessment.
- CTA for LAA exclusion (subjects who had AtriClip placed during the Epicardial Surgical Ablation Procedure). Images will be sent to a core lab.
- CTA imaging pulmonary veins should be performed for assessment of pulmonary vein stenosis. Imaging will be sent to a core lab if the subject is symptomatic for PV stenosis.
- (Note: CT/MRI is acceptable method for PV imaging if the subject did not have an AtriClip placed during the Epicardial Surgical Ablation period. In that case, use the same imaging technique performed at baseline PV imaging to the extent possible. If subject cannot tolerate CTA, a TEE is also an acceptable method to assess for LAA exclusion.)

7.15 Visits 12, 13, 14, and 15 (2, 3, 4, and 5 years Post Endocardial EP Ablation Procedure) – Annual Follow-Up Visits

A follow-up evaluation will be scheduled for the **annual follow up visits (\pm 60 days)**. The following will be conducted and/or obtained at the annual follow up visits:

- Medications Review
- 24-Hour Continuous ECG Monitoring/ Arrhythmia Monitoring - Holter or ZioTM Patch
- Emergency room visits for atrial fibrillation, atrial flutter, and atrial tachycardia
- Hospital re-admission for atrial fibrillation, atrial flutter, and atrial tachycardia
- Incidence of atrial fibrillation, atrial flutter, and atrial tachycardia that require treatment
- Pacemaker implantation
- Additional catheter ablations
- Incidence of DC cardioversion to address Atrial Dysrhythmia
- Incidence of stroke or TIA

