CTA/CT/MRI/TTE/TEE – These procedures will be conducted according to the site's institutional SOC. Depending on the parameter being measured or the subject requirements, equivalent or superior diagnostic procedures can be utilized as long as the required data can be adequately obtained and is in the protocol required time window. For example, if CTA cannot be performed (i.e., patient is allergic to contrast media or has poor kidney function), TEE is also acceptable to verify exclusion of the LAA. The PI should document the acceptability of any alternate diagnostic procedures.

LAA Exclusion –An independent imaging laboratory will be utilized for assessment of the complete exclusion of the LAA defined by lack of fluid communication (<3 mm residual

communication with LAA and < 10mm residual pocket) between the LA and LAA confirmed by TEE, CTA or MRI evaluation.

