9.8 Analysis of Secondary Endpoints

An exact, one-sample binomial test will be conducted at a one-sided $\alpha=0.025$ level of significance to test the following hypothesis that the proportion of subjects in the AtriClip effectiveness population with LAA exclusion at the 12-Month Visit (15 months post AtriClip placement) is significantly higher than 80%:

$$H_0 : p_2 \leq .80 \quad vs. \quad H_a : p_2 > .80$$

The last observation carried forward (LOCF) method will be utilized for patients who do not have TEE testing at the 12-Month Visit. This method is considered conservative based on the EXCLUDE study³⁵, which showed a higher exclusion rate at 3 months than at the time of clip placement (98.4% vs. 95.7%).

The remaining secondary endpoints will be exploratory and as such, the data will be tabulated without formal statistical testing.

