11.3 Core Laboratories

ECG Core Laboratory

An independent ECG core laboratory will be utilized for assessment of the following data collected on subjects. All data submitted to the core laboratory will be reviewed and the core laboratory will interpret the reading.

- Visit 10 and Visit 11: ECG collected at follow-up study visits
- Visit 10 and Visit 11: Continuous ECG monitoring recordings (Holter or ZioTM Patch)
- Visit 10 thru Visit 11: Symptom driven monitoring

All ECG monitoring shall be performed in accordance with the core laboratory's recommended protocol which is provided to the sites in the Study Reference Manual.

Imaging Core Laboratory

Left Atrial Appendage: An independent core laboratory will be utilized for assessment of the complete exclusion of the LAA defined by lack of fluid communication (<3 mm residual communication with LAA and < 10mm residual pocket) between the LA and LAA.

Images to be sent by the site include:

- Visit 5: (TEE) Endocardial Procedure Visit
- Visit 11: (CT/CTA/MRI) 12-month post Endocardial Procedure Visit.

Pulmonary Veins: If a subject exhibits symptoms suggestive of pulmonary vein stenosis, the baseline and subsequent CT/MR imaging will be submitted by the site to an independent imaging core laboratory for analysis.

- Images sent to core lab (as applicable) for Visit 4, Visit 10, Visit 11

Consistent with the recommendation from the 2012 HRS/EHRA/ECAS Expert Consensus Statement in Surgical and Catheter Ablation of AF, PV stenosis is categorized as mild < 50%, moderate 50-70% and severe ≥ 70% reduction in the diameter of a PV or PV branch.

Esophagoscopy Core Laboratory

Esophagoscopy (EGD): An independent core laboratory will be utilized for adjudication of any esophageal injuries discovered on the post epicardial procedure EGD. All data submitted to the core laboratory will be reviewed and the core laboratory will provide adjudication. An esophagoscopy at Visit 2 will be performed as a baseline assessment. An esophagoscopy at Visit 3 is to be performed 24 to 72 hours post Procedure. If the esophagoscopy at Visit 3 reveals a new acute esophageal injury, subject reports, images, data and relevant documents will be submitted to a core lab.

REFERENCE LIST

¹

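### The carry-forward rule for the labeling test of 12-month LAA exclusion is triggered by a missing TEE, but the scheduled 12-month test is CTA

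*SAP*

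**What the plan says.** **The trigger.** For the tested endpoint, SAP 5.6.3.1 says "The LOCF method will be utilized for patients who do not have TEE testing at the 12-Month visit". Protocol 9.8 applies last observation carried forward (LOCF) in the same terms: it is "utilized for patients who do not have TEE testing at the 12-Month Visit".

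**The scheduled test.** Protocol 7.14 lists for Visit 11 "CTA for LAA exclusion (subjects who had AtriClip placed during the Epicardial Surgical Ablation Procedure). Images will be sent to a core lab". Footnote 18 of the Schedule of Assessments agrees: "CTA imaging of the LAA performed only in those subjects that had the AtriClip placed during the Epicardial Surgical Ablation Procedure". TEE at that visit is conditional: "If subject cannot tolerate CTA, a TEE is also an acceptable method to assess for LAA exclusion" (7.14). Protocol 7.19 also accepts TEE where CTA cannot be done, and has an independent laboratory judge exclusion as "confirmed by TEE, CTA or MRI evaluation". The imaging list in Protocol 11.3 gives "Visit 11: (CT/CTA/MRI) 12-month post Endocardial Procedure Visit" and, for the endocardial procedure, "Visit 5: (TEE) Endocardial Procedure Visit".

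**The general rule.** Protocol 9.9 and SAP 5.3 apply LOCF to the LAA endpoints for missing values, without naming a modality. Their definition of LOCF concerns a subject who lacks a scheduled test.

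**The justification.** Protocol 9.8 calls LOCF conservative because an earlier AtriClip trial showed 95.7% exclusion at placement and 98.4% at 3 months.

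**The concern.** The sentence that decides whose result is carried forward names a test that most patients are not scheduled to have at 12 months. A patient who attends Visit 11 and has the planned CTA has no 12-month TEE, and so meets the trigger. The value carried forward would normally be the Visit 5 TEE, taken about three to four months after clip placement. Protocol 9.6.1 fixes the endpoint at about 15 months after placement. Followed to the letter, the test would mostly judge exclusion at the endocardial procedure and report it as exclusion at 12 months.

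This matters because the test supports a labeling claim, and because the error stands in the endpoint-specific text, which an analyst would normally follow ahead of a general section.

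**Working it through.** **1. The plan's own figure.** Protocol 9.6.1 supports the 80% goal with a lower 95% exact limit of just under 88% for the earlier trial's 67/70. The Clopper-Pearson lower limit is the 2.5% quantile of Beta(67, 4) = 0.8798. The figure reproduces.

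**2. The passages set side by side.**

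| Patient at Visit 11 | Endpoint-specific sentence (SAP 5.6.3.1, Protocol 9.8) | General rule (SAP 5.3, Protocol 9.9) |
|---|---|---|
| CTA as scheduled | LOCF | CTA result used |
| CT or MRI | LOCF | that result used |
| TEE as fallback | TEE result used | TEE result used |
| No image | LOCF | LOCF |

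The two rules disagree for every patient imaged by anything but TEE, which includes those imaged as scheduled.

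**3. What the literal reading would do.** Inputs from the documents: p0 = 0.80, one-sided 0.025, exact binomial test (SAP 5.6.3.1); at most 220 treated (SAP section 4); N = 182 from the effectiveness calculation (Protocol 9.3), used here as a smaller population. Assumptions: size of the clip population n (not given), share f with a 12-month TEE from 0 to 20%, and carried-forward rate r.

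The critical count is the smallest c with P(Bin(n, 0.80) ≥ c) ≤ 0.025.

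- n = 220: 187 gives 0.0350 and 188 gives 0.0232, so c = 188 (85.5%).
- n = 182: c = 157 (86.3%), size 0.0184.

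Under the literal rule the number of successes is A + B, with A ~ Bin(fn, 0.80) for patients who have a 12-month TEE and B ~ Bin(n − fn, r) for everyone else. The chance of declaring success when the true 12-month rate is 80% is P(A + B ≥ c). The ranges run from f = 20% to f = 0.

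| r | n = 220 | n = 182 |
|---|---|---|
| 0.80 (no change over time) | 0.023 | 0.018 |
| 0.85 | 0.315–0.471 | 0.236–0.362 |
| 0.88 | 0.701–0.895 | 0.577–0.801 |
| 0.90 | 0.897–0.988 | 0.805–0.959 |
| 0.957 | about 1.00 | about 1.00 |

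For example, with n = 220, f = 20% and r = 0.90, the analysed rate is (44 × 0.80 + 176 × 0.90)/220 = 0.88, above the 85.5% needed. At r = 0.80 the sum is again Bin(n, 0.80), so the size is unchanged.

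**4. The claim that LOCF is conservative.** The cited data are 67/70 at placement and 60/61 at 3 months. They say nothing about months 3 to 15, and the endpoint lies at about month 15.

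**The case against.** The strongest reply is that the intent is clear. SAP 5.3 and Protocol 9.9 reserve LOCF for missing values, SAP 5.6.3.1 defines the proportion at the 12-month visit, and Protocol 7.19 accepts several modalities. SAP 5.6.3 also plans summaries of observed data, so a discarded CTA would show. On this view one modality word is wrong. That stands as to intent and likely conduct. It does not repair the sentence, which is repeated in both documents and governs a labeling test.

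A reader might infer more than the documents support:

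- *That the labeling test will run at these false-success rates.* The table shows only what literal application would do if exclusion fell to 80% by 12 months. The documents show no such decline.
- *That LOCF inflates the test for patients who truly have no 12-month image.* That is a separate question and also needs a decline. The attrition of approximately 20% in Protocol 9.3 concerns the primary effectiveness endpoint, not missing LAA images.
- *That patients who never reach the catheter stage can only have their intra-operative TEE carried forward.* Protocol 9.2.1 says continued follow-up will be attempted in such patients. It does not mention LAA imaging, so the point is open.
- *That a fallback TEE would go without an independent reading.* Protocol 7.19 and schedule footnote 3 already send LAA exclusion to a core laboratory, and the list in 11.3 need not be exhaustive.

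**Conclusion.** The trigger is wrong as written in SAP 5.6.3.1 and Protocol 9.8, and it contradicts both the visit schedule and the general missing-data rule. It should be corrected before analysis. The contradiction itself rests on no assumption.

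Its possible size does rest on assumptions. With 220 clip patients, a true 12-month rate of 80% and up to 20% having a 12-month TEE, literal use would give false success of about 32–47% at a carried-forward rate of 85% and 90–99% at 90%, instead of 2.3%. If exclusion is stable there is no inflation. The likelier outcome is that an analyst uses the CTA and thereby departs from the pre-specified sentence.

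Two smaller points go with it. The word *conservative* in Protocol 9.8 is not supported beyond 3 months. And SAP 5.3 applies LOCF to all LAA endpoints, while SAP 5.6.3.2 excludes missing observations for endpoint #2.

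**What to change.** 1. In SAP 5.6.3.1 and Protocol 9.8, make the trigger: *have no evaluable 12-month LAA imaging by any accepted modality (CTA, CT, MRI or TEE)*. State that an available 12-month result is always used. Do not rank the modalities in this sentence. A condition such as CTA having been impossible could again send a validly imaged patient to LOCF.
2. Keep LOCF as the primary rule for patients with no 12-month image.
3. Qualify *conservative* in Protocol 9.8: the cited data end at 3 months and the endpoint is at about 15.
4. Reconcile SAP 5.3 with SAP 5.6.3.2 for endpoint #2. It is exploratory, so either rule will do if only one is stated. Protocol 9.9 carries the same general sentence as SAP 5.3 and should match.
5. Optional: one supportive table that counts patients with no 12-month image as not excluded and gives the break-even count, as SAP 5.3 already defines for primary effectiveness.

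Items 1 to 4 are wording changes and need no new data. The optional table may give a less favourable estimate. Assuming n = 200 (172 successes needed) and 10% without an image, it would require 172/180 = 95.6% among those imaged. At 90% observed (162 of 180), break-even is 172 − 162 = 10 of the 20 missing. It should therefore stay supportive.
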